7.3.2. Alcohol calendar– Time-Line Follow-Back

Time-Line Follow-Back (TLFB) is a method that can be used to obtain information about patients' alcohol consumption. (Sobell, Maisto et al 1979). In short, it means that as far back as 3 months ago, you retrospectively reconstruct how many standard glasses you have consumed per day. It is accepted that the reporting is not an exact representation of the alcohol intake, but also that it

provides a decent benchmark, which is also sensitive to changes in the drinking pattern. An alcohol calendar (see Appendix C) is used for this purpose. For study purposes, alcohol consumption reported via TLFB is used for the 4 weeks preceding each visit. How to determine the TLFB at baseline is stated in section 8.1.2.

When filling in TLFB, the patient and therapist must consult and results of blood tests and for the intervention arm, TripleA measurements must also be taken into account to identify if and when alcohol intake has occurred.

Information about missed measurements or measurements that show alcohol in the exhaled air (both for TripleA and for regular measurements at the care provider) should be used in the TLFB call and should in the alcohol calendar correspond to a number greater than 0 standard glasses on the current day. There may be discrepancies between what the patient is willing to state in the TLFB and the information that the caregiver has available in the TripleA caregiver portal or from other sources. The caregiver should talk to the patient about this, and give the patient the opportunity to update the information in the TLFB if necessary, but should not force the patient to enter a number greater than 0 or change information provided by the patient without the patient's consent.

In CRF, it is possible for the care provider to state whether there are signs of alcohol intake that do not correspond to reported intake in TLFB.

Time: At each visit.

AUDIT (The Alcohol Use Disorders Identification Test)

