7.3.7. Biological samples (blood and urine)

Samples are ordered via the medical record system, taken and handled according to regular clinical routine. Patients are instructed to leave the samples some week before the visits, so that test results are available for the visit.

For sampling instructions, refer to the latest updated versions on the Academic Laboratory's website.

Urine samples for drug screening usually include amphetamine, benzodiazepines, burprenorphine, cannabis, cocaine, methadone metabolites, opiates. Verification analysis in the event of a positive result on a urine dipstick is performed if clinically relevant

Time: Done at visit 1

Phosphatidylethanol (PEth) is analyzed at Karolinska Laboratory. The concentration of PEth-16:0/18:1 is given in the unit $\mu\text{mol} / \text{L}$. The PEth level in the blood reflects the alcohol consumption of recent weeks. PEth-16:0/18:1 values lower than $0.05 \mu\text{mol} / \text{L}$ indicate no or low sporadic alcohol consumption. Values between $0.05-0.30 \mu\text{mol} / \text{L}$ speak for regular moderate consumption, but even occasional very large intakes of alcohol can probably give measured values in this range.

Time: Made at each visit

Low carbohydrate transferrin (CDT) shows alcohol-induced change in the glycosylation pattern of transferrin, which is measured in serum samples. CDT is used as a marker to demonstrate regular alcohol consumption and «risk use / abuse», where the measured value reflects the intake during the last weeks - the month. Single major alcohol intakes do not affect CDT levels.

Analyzed at the Academic Laboratory and reported in%. Reference interval $<2.0\%$.

Time: Made at each visit

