7.8.3.2. Measures in the event of noted deviations in the care provider portal

Deviations in the form of a positive or missed sobriety test must be discussed with the patient at the visit and allowed to influence the TLFB responses.

The caregiver has the opportunity to enter status comments for an individual test, which means that the database will contain supplementary information - without overwriting the basic status. The following options are available:

If the basic status is "Missed", the following status comments can be selected:

- No alcohol
- Alcohol could not be excluded
- Technical issue.

If the default status is "Alcohol could not be excluded", the following status comments can be selected:

- No alcohol
- Technical issue.

If the basic status is "Technical error", the following status comments can be selected:

- No alcohol
- Alcohol could not be excluded

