We will initially summarize data from the TripleA alcohol tests as the proportion of sober days (both based on tests performed and corrected values (as above)) over a 4-week period immediately before a visit (1, 2, 3, 6.11 months). A positive alcohol test is > 0.10 mg / L alcohol in the breath test. The effect will be calculated against TLFB data transformed in a similar way. We will also perform correlation studies between TripleA and reported levels of PEth and CDT in blood samples.

The primary and secondary efficacy measures analyzed based on TLFB data will be compared with corresponding analyzes that also take into account blood test data and TripleA results.

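### Section 9.1.3 compares TripleA with a TLFB calendar that TripleA and blood results helped to fill in, so the two sources are not independent

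*Combined protocol and SAP*

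**What the plan says.** **The comparisons.** Section 9.1.3 reduces the TripleA tests to the proportion of sober days in the four weeks before a visit, once from performed tests and once from values corrected by the caregiver. It continues: "The effect will be calculated against TLFB data transformed in a similar way". The TLFB-based primary and secondary measures "will be compared with corresponding analyzes that also take into account blood test data and TripleA results". Separately, TripleA is to be correlated with PEth and CDT.

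**How the calendar is filled in.** Section 7.3.2 (in rough translation) says that "the patient and therapist must consult and results of blood tests" are to be used, and that "for the intervention arm, TripleA measurements must also be taken into account to identify if and when alcohol intake has occurred". A missed test, or one showing alcohol, should appear in the calendar as more than zero glasses that day. Section 7.8.3.2 adds that positive or missed tests "must be discussed with the patient at the visit and allowed to influence the TLFB responses". Section 7.3.7 has blood samples given ahead of the visit "so that test results are available for the visit".

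**The limits on this.** Under 7.3.2 the caregiver raises a discrepancy but may not press for or make a change without the patient's consent. The CRF has room to note signs of intake that the calendar does not reflect. For TripleA, 9.1.2.2 states that the original test status is always retained after reclassification. No such rule is given for the calendar, and no section provides for one completed before the results are seen.

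**The concern.** Setting TripleA against TLFB is informative only if the calendar says something that TripleA has not already told it. Here the interview is designed to move the calendar towards the TripleA record. Agreement found afterwards mixes two things: what the patient would have reported unaided, and what the patient accepted when shown the result. The CRF note records only disagreement that survives the conversation, so it cannot recover days that were changed during it.

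Two conclusions are at risk. The report could say that TripleA agrees well with self-report when part of that agreement arose in the interview. It could also say that adding blood and TripleA data changes the efficacy results little, when those data had already entered the calendar. The second problem differs by arm, because TripleA informs the calendar only in the TripleA arm while blood results inform it in both.

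**Working it through.** **The plan's own figures.** The documents give no agreement figure, so there is none to reproduce. The sample size does not depend on this point. It reproduces with the pooled-variance formula: [1.960·√(2·0.45·0.55) + 0.842·√(0.21 + 0.24)]² / 0.30² = 41.97, so 42 per group; 42/0.8 = 52.5, so 53 per group and 106 in total.

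**Illustration of the mechanism.** All inputs are assumptions. D is the share of drinking days, u the share of these the patient would report unaided, and s the day-level sensitivity of TripleA. f = 1% is its false-positive rate on sober days. a is the share of flagged days (TripleA positive, calendar zero) that the patient agrees to revise. The unaided calendar is assumed to contain no false reports of drinking. Ignoring missed tests, the day-level cells are:

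- both positive: D·s·[u + (1−u)a] + (1−D)·f·a
- TripleA only: D·s·(1−u)(1−a) + (1−D)·f·(1−a)
- TLFB only: D·(1−s)·u
- neither: the remainder

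Kappa = (Po − Pe)/(1 − Pe). For D = 25%, u = 60%, s = 75%:

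- a = 0: cells 0.1125, 0.0825, 0.0375, 0.7675. Po = 0.880; Pe = 0.195·0.150 + 0.805·0.850 = 0.7135; kappa = 0.1665/0.2865 = 0.58.
- a = 80%: cells 0.1785, 0.0165, 0.0375, 0.7675. Po = 0.946; Pe = 0.195·0.216 + 0.805·0.784 = 0.6732; kappa = 0.2728/0.3268 = 0.83.

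| D | u | s | a = 0 | a = 20% | a = 50% | a = 80% |
|---|---|---|---|---|---|---|
| 25% | 60% | 75% | 0.58 | 0.65 | 0.75 | 0.83 |
| 25% | 80% | 75% | 0.70 | 0.73 | 0.78 | 0.83 |
| 15% | 50% | 70% | 0.51 | 0.61 | 0.73 | 0.83 |

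At 80% acceptance the three rows can no longer be told apart, although unaided disclosure ranges from 50% to 80%.

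**Missed tests can reverse the direction.** Suppose a test is missed on 30% of drinking days and 15% of sober days, such days count as sober for TripleA, and the patient accepts a share a of them as drinking days. The first two cells keep their form, with the drinking-day terms multiplied by 0.70 and the sober-day terms by 0.85. The TLFB-only cell becomes D·0.70·(1−s)·u + D·0.30·[u + (1−u)a] + (1−D)·0.15·a. In the first scenario:

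- a = 0: cells 0.0788, 0.0589, 0.0713, 0.7911; Po = 0.8699; Pe = 0.7537; kappa = 0.47.
- a = 80%: cells 0.1259, 0.0118, 0.1853, 0.6771; Po = 0.8030; Pe = 0.6369; kappa = 0.46.

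The other two scenarios go from 0.55 to 0.46 and from 0.43 to 0.39.

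**A second set of assumed inputs.** Drinking on 30% of days; a test missed on 30% of drinking and 5% of sober days; TripleA sensitivity 80%, false positives 1%; unaided TLFB specificity 98% and sensitivity 40%, 60% or 80%. Kappa, from no flagged day revised to all revised:

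| Days with a missed test | TLFB sensitivity 40% | 60% | 80% |
|---|---|---|---|
| counted as positive | 0.36 to 0.93 | 0.52 to 0.91 | 0.65 to 0.89 |
| excluded | 0.41 to 0.90 | 0.57 to 0.87 | 0.69 to 0.85 |
| counted as sober | 0.34 to 0.60 | 0.45 to 0.59 | 0.53 to 0.57 |

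When missed days count as sober, the sign therefore depends on inputs such as how often sober days contain a missed test.

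**The case against.** Several stronger readings are tempting, and the objections to them stand.

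- *The calendar has been corrected to TripleA.* Section 7.3.2 forbids changes without consent. Revision is partial, and the acceptance rate is unknown.
- *Agreement is always overstated.* It is not: where missed tests count as sober, kappa can fall, as shown above.
- *The first answers are thrown away.* The documents are only silent. Section 7.3.2 speaks of the patient updating entries, and data handling is left to a separate data management plan (section 10).
- *The added-data analysis is circular.* It asks whether evidence the patient did not accept would change the result, which is a fair robustness question for a reconciled calendar.
- *The data cannot show what TripleA adds.* Raw TripleA status is kept, and its correlation with PEth and CDT does not pass through the calendar.

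It is also true that 9.1.3 names no agreement statistic and works with four-week proportions, not days. If all patients under-report by a similar fraction, a correlation of proportions is already high without any prompting and has less room to rise than kappa. Section 7.8.11 does acknowledge that TripleA may change TLFB reporting, but as a bias between arms and not as a limit on 9.1.3.

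None of this removes the dependence. It limits what can be said about its size and, for one treatment of missed tests, its direction.

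**Conclusion.** The point holds in a limited form. The TripleA–TLFB comparison in 9.1.3 is not between independent sources, because the protocol requires TripleA and blood results to inform the calendar and provides for no unaided version. Agreement is biased upward on performed tests or with missed tests counted as positive; with missed tests counted as sober it may move either way. The added-data analysis will tend to understate the contribution of the extra data, more so where TripleA has already fed the calendar.

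The size cannot be derived from the documents. The kappa values rest wholly on assumed drinking frequency, disclosure, test accuracy and acceptance, and on a day-level statistic the plan does not name.

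A reader might infer that the primary result is invalidated. This point does not support that: the analyses are exploratory, and the primary endpoint and sample size are unaffected. The change is still worth making, since unaided answers that were not recorded cannot be recovered after the visit.

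**What to change.** 1. At each follow-up visit, in both arms, have the patient complete the Appendix C calendar before portal or blood results are shown, and lock it in the CRF.
2. Then make the reconciled calendar as 7.3.2 describes. It remains the source for the primary and secondary endpoints.
3. In 9.1.3, use the unaided calendar for TripleA–TLFB and any biomarker–TLFB comparison. Pair it with uncorrected TripleA status, because the corrected status can reflect the patient's explanation or extra PEth/CDT samples. State how days with a missed test are classified, and report the number of revised days by arm.
4. State that the unaided calendar in the TripleA arm is still affected by awareness of being monitored, as 7.8.11 recognises. The change removes the direct feedback, not that influence.
5. If this is not done, label the TripleA–TLFB results as non-independent and do not interpret them as agreement with self-report. PEth and CDT cannot take over as a day-level reference: by sections 4.6 and 7.2.2, PEth does not detect occasional intoxication and single large intakes do not move CDT.

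Cost: one extra copy of an existing one-page form and a little more time at each visit.

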9.2. Sample size, significance level and statistical strength

The primary endpoint is the proportion of patients who do not have heavy drinking days during a 4-week period after 12 months from baseline. Assuming that the proportion is 30% in the control group and you want to be able to detect a difference of 30% between the TripleA and the control group, 42 patients are needed per treatment group to achieve a strength of 80% with a double-sided test of 5% significance level. Assuming that the proportion of patients who do not complete the study is about 20%, a total of 106 patients need to be randomized, ie 53 per group.

Expected loss

The drop-out rate in alcohol studies is usually quite large.

At inclusion, the patient is asked to provide at least one contact person that the study staff can contact if the patient is absent from agreed meetings, interrupts treatment and / or stops blowing. Patients who do not wish to continue their treatment should be informed that they are welcome to continue using TripleA and / or alcohol, or otherwise report their alcohol consumption, as this is valuable information for the study. If the patient wants to stop the study completely, the study staff should at least ask the question "how many standard glasses have you drunk the most in one day since we were last seen?". This gives the opportunity to assess whether there has been a heavy drinking day or not.

A certain loss of patients during the course of the study is expected. Three types of missing data can be identified.

1. Patients who choose to discontinue treatment and study participation.
2. Patients who choose to discontinue treatment but who continue to provide information on alcohol intake (i.e. remain in the study)

Patients who continue treatment but who do not provide complete information on alcohol intake.

4. Patients who miss occasional visits.

All efficacy evaluations will be performed on two analysis populations, a population consisting of all randomized patients contributing efficacy data from at least one baseline visit (ITT) and a population consisting of all patients who completed the study according to the protocol (PP).

In the first population, missing values will be handled primarily according to the principle of multiple imputation (MI). In this approach, the missing values according to type 1 in the list above will be directly imputed according to the MI principle while values of type 2 in the list above, i.e. which are collected after treatment interruption, will remain as missing values, which are then imputed. Missing values of type 3 in the list above, ie. incompletely completed alcohol intake data, are replaced according to the principles described for each variable in section 8.3, ie. in these situations there is data and thus MI does not need to be used. For missing values of type 4 in the list above, MI is used.

In addition to the MI approach, any exploratory analyzes will be made where the principle of last-observation-carried-forward (LOCF) can be used, as well as an analysis where only observed values are included in the evaluation.

In addition to the above, a separate evaluation will be made for patients according to type 2 in the list above where collected values after treatment interruption are used. When tabulating alcohol intake data from visit 1 to visit 6, this group will be reported on three lines where line 1 indicates the number of patients in this group who remain on the treatment at each visit, while line 2 indicates the number of patients in this group who discontinued treatment from each visit. The third row then constitutes the sum of row 1 and row 2, i.e. the whole group of patients in the active group who discontinued treatment at some point after visit 1 but still remained in the study.

The analyzes performed on the ITT population will be considered as the primary ones.

The safety assessment will be based on the ITT population.

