7.5. Loss

7.5.1. Loss of patients

The reason why a patient discontinues treatment or study must be documented and these patients must be followed up. Patients who discontinue the study will not be reimbursed. The loss will be reported.

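### The primary ITT analysis discards drinking data collected after treatment interruption and imputes over them, so under ordinary imputation it leans toward an undeclared on-treatment effect

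*Combined protocol and SAP*

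**What the plan says.** Section 9.2 (Expected loss) lists kinds of missing data. Type 1 patients leave both treatment and study. Type 2 are "Patients who choose to discontinue treatment but who continue to provide information on alcohol intake" and so remain in the study. Type 4 patients miss occasional visits. Multiple imputation is the main method in the ITT population, and the ITT analyses are the primary ones. Type 1 and type 4 values are imputed. Type 2 values, "which are collected after treatment interruption, will remain as missing values, which are then imputed". The rule covers all efficacy evaluations, including the primary endpoint of sections 7.2.1 and 9.1.2.1: no heavy drinking days in the four weeks before the 12-month visit.

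Elsewhere the plan asks for these data. Section 7.5.1 states: "The reason why a patient discontinues treatment or study must be documented and these patients must be followed up". Section 9.2 invites patients who stop treatment to keep using TripleA "or otherwise report their alcohol consumption, as this is valuable information for the study".

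Two further analyses in section 9.2 may use the collected values. One is introduced by "In addition to the MI approach, any exploratory analyzes will be made" and includes "an analysis where only observed values are included in the evaluation". The other is described as "a separate evaluation will be made for patients according to type 2 in the list above".

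**The concern.** An analysis called ITT is normally read as comparing the arms as randomised, whatever happened to treatment afterwards. Here observed primary outcomes of randomised patients still under follow-up are removed and replaced by predictions. If those predictions come from patients who stayed in treatment, the estimate approaches the difference that would be seen if nobody had interrupted. That is a different question, and the plan does not say it is asking it.

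Retention is part of what TripleA is meant to change: section 6.1.2 makes fewer discontinuations an objective, and section 7.8.11 expects more patients to complete treatment. Retention is recorded at each visit (7.2.2) and compared by a log-rank test (9.1.2.2, item ix), so it is not lost to the trial. But that comparison shows who stayed, not how those who left were drinking. If better retention also lowers heavy drinking at 12 months, the primary endpoint can miss that part of the benefit. In other circumstances the rule overstates the benefit.

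**Working it through.** **The plan's own figure.** Inputs from section 9.2: control 30%, difference 30 points (so 60% on TripleA), two-sided 5%, power 80%, 20% non-completion. With the pooled two-proportion formula,

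n = [1.960 × √(2 × 0.45 × 0.55) + 0.842 × √(0.3 × 0.7 + 0.6 × 0.4)]² / 0.30² = 41.97, so 42 per arm; power at 42 is 0.800; 42/0.8 = 52.5, so 53 per arm and 106 in all.

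This reproduces and is not disputed.

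**Effect of the rule.** Everything here except the 60% and 30% is assumed, and treating those two as on-treatment rates is also an assumption. Let s be the type 2 share in an arm, p the on-treatment rate of no heavy drinking days, and q the rate in interrupters. Leave type 1 and type 4 aside.

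- As-randomised rate in an arm: (1 − s)p + sq.
- Rate after within-arm imputation from on-treatment values: about p.
- Shift in the difference (planned minus as-randomised): s_T(p_T − q) − s_C(p_C − q).

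| Case | p, TripleA / control | q | s, TripleA / control | As-randomised | Planned |
|---|---|---|---|---|---|
| 1 | 60% / 30% | common | 5% / 5% | 28.5 | about 30 |
| 1 | 60% / 30% | common | 10% / 10% | 27 | about 30 |
| 1 | 60% / 30% | common | 20% / 20% | 24 | about 30 |
| 2 | 45% / 45% | 10% | 10% / 20% | 3.5 | about 0 |
| 2 | 45% / 45% | 10% | 10% / 30% | 7 | about 0 |
| 3 | 60% / 30% | 10% | 10% / 25% | 30 | about 30 |
| 4 | 60% / 30% | 10% | 5% / 25% | 32.5 | about 30 |

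Examples: case 1 at 20% with q = 10% is 0.50 − 0.26 = 0.24; case 2 at 10% / 30% is 0.415 − 0.345 = 0.07. In case 1 the common q cancels. The shift is also nil if interrupters keep their arm's on-treatment rate. For scale, the standard error at 42 per arm is √((0.24 + 0.21)/42) = 0.1035, about 10 points.

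**Does conditioning on earlier drinking repair it?** Suppose imputation is by arm and an earlier binary TLFB status. Let 40% of each arm have the favourable earlier status, and let the chance of that status given the 12-month outcome be the same in interrupters and others. For odds ratios of 4, 9, 20 and 40 between earlier status and month 12, the large-sample results in points are:

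- Case 1 at 20% per arm: 29.4, 28.7, 27.9, 27.3, against 24.
- Case 2 at 10% / 30%: 0.8, 1.7, 2.8, 3.7, against 7.

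With 30% to 50% having the favourable status, an odds ratio of 40 gives 29.0 to 26.1 and 3.6 to 3.0. The gap narrows but does not close.

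A separate large-sample simulation let interruption depend on month-6 status, imputed by arm and month-6 status, and used off-treatment rates of 10% to 30% unrelated to that status. It returned 0.30 throughout, against as-randomised differences of 0.22 to 0.28.

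**The case against.** The strongest reply is that harm is conditional. The documents give no type 2 share, no off-treatment rate and no imputation model. At 5% to 10% interrupters, case 1 moves by 1.5 to 3 points beside a standard error of about 10. The result also leans on equal off-treatment rates: at 20% per arm with control q at 10%, the 6-point gap falls to 4, 2 and 0 as the TripleA q rises to 20%, 30% and 40%. All of this stands, and no direction can be claimed. But the shift is systematic, and the rule decides which question the primary result answers, whatever its size.

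Second, the handling is openly prespecified, and an on-treatment target can be legitimate if labelled. True, but it carries the ITT label and no such target is stated. The observed-values analysis is exploratory, omits patients without data and does not say whether post-interruption values count. The type 2 evaluation describes a subgroup formed after randomisation. Neither is the as-randomised comparison.

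Third, treatment interruption is undefined. A patient may stop conventional treatment and keep TripleA, so even device users' outcomes could be set to missing. This stands and belongs in the fix.

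Fourth, keeping type 2 values does not fully recover the as-randomised effect, because type 1 patients are still imputed. With 60% / 30%, q = 10%, 20% type 1 and 5% type 2 in each arm, the as-randomised difference is 0.475 − 0.25 = 22.5 points. The plan gives 30. Keeping type 2 values, without treatment status in the model, gives (0.455 − 0.23)/0.80, about 28. The change moves the estimate the right way; treatment status in the imputation model is needed to go further.

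**Conclusion.** The concern holds and should be corrected before analysis. That the primary ITT analysis deletes collected outcomes follows directly from section 9.2 and needs no assumption. That it leans toward an on-treatment effect rests on ordinary missing-at-random imputation within arm; the plan specifies no alternative such as reference-based or off-treatment imputation. The size rests wholly on assumed shares and rates: in the cases shown, from 6 points too favourable, through nil, to 7 points too unfavourable.

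**What to change.** In section 9.2:

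1. Use every 12-month TLFB value collected in the primary ITT analysis, whether or not treatment was interrupted.
2. Apply multiple imputation only to values not collected (types 1 and 4). Include the collected post-interruption values in the imputation data, and state the model's variables, including treatment status.
3. Define treatment interruption: conventional treatment, TripleA, or either.
4. Keep the present type 2 rule as a supplementary analysis, labelled as a hypothetical on-treatment effect.
5. Say whether the target in "you want to be able to detect a difference of 30% between the TripleA and the control group" is the as-randomised difference, and whether the 20% non-completion includes type 2 patients.

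**Cost.** No new data collection. Power depends on point 5. The figures below use the pooled formula, count observed outcomes only, and take 10% and 20% type 2 per arm with case 1 rates and q = 10% (differences of 27 and 24 points).

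- Type 2 on top of the 20%, the plainer reading because these patients remain in the study: 42 observed per arm gives about 72% and 62%. With their data deleted, about 37 and 32 per arm give about 75% and 68% for 30 points.
- Type 2 within the 20%: about 48 and 53 observed per arm give about 77% and 73%, against 80% for 30 points at 42.
- Type 2 within the 20% and 30 points already the as-randomised target: power rises to about 85% and 88%.

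The reason for the change is the question answered, not power.
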